12.2 DEFINITIONS

12.2.1 ADVERSE EVENT

An adverse event (AE) is defined in ISO 14155:2011 as any untoward medical occurrence, unintended disease or injury, or untoward clinical signs (including abnormal laboratory finding) in subjects, users or other persons, whether or not related to the investigational medical device.

Note: anticipated adverse events are adverse events that have been identified as possible adverse events related to the investigational medical device or the study procedure. The anticipated events of this clinical study are outlined in Section 3.1, Potential Risks

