12.2.2 ADVERSE DEVICE EFFECT

An adverse device effect (ADE) is defined in ISO 14155:2011 as any adverse event related to the use of an investigational medical device. This definition includes:

- Adverse event resulting from insufficient or inadequate instructions for use, deployment, implantation, installation, or operation, or any malfunction of the investigational medical device.
- Any event resulting from use error or from intentional abnormal use of the investigational medical device.

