
Heart Failure
	
Heart Failure - A progressive condition that involves loss of pumping ability by the heart (heart muscle weakens and gradually loses its ability to pump enough blood through the body), generally accompanied by fluid accumulation in body tissues, especially the lungs.
 
Heart Failure Hospitalization - An unplanned hospitalization that results in at least one overnight stay (i.e., where the admission date and the discharge date are different) that includes increased signs and/or symptoms of worsening heart failure and requires the administration or augmentation of existing heart failure therapy.
 
Severe Heart Failure – See NYHA Class IV

HEART Team
	
The ‘HEART Team’, for the purpose of this study, must include a minimum of one Cardiologist, and one Cardiac Surgeon.

Hemolysis (Device Hemolysis)	
Rupturing of red blood cells (erythrocytes) and the release of their contents (cytoplasm) into surrounding fluids.
 
Device hemolysis is defined as hemolysis in or near the investigational device that interferes with the function of the device. Device hemolysis related thrombus may be confirmed by operation, autopsy, or diagnostically by such methods as echocardiography, angiography, or magnetic resonance imaging.

Implant procedure	Placement of the investigational device in the tricuspid valve regurgitant orifice.
Infection	Known infection requiring intravenous antibiotics for other than prophylaxis, and/or extended hospitalization.
INR	International normalized ratio
IVC	Inferior vena cava
KCCQ	Kansas City Cardiomyopathy Questionnaire is a health-related quality-of-life measure for patients with congestive heart failure.
LVEF	Left ventricular ejection fraction
Malfunction	Refer to ISO 14155 definition
Myocardial Infarction	Refer to VARC-2 definition

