Screen Failure	A patient who has signed the consent but, does not meet the inclusion criteria or who meets at least one of the exclusion criteria.
Serious Adverse Device Effect (SADE)	Refer to ISO 14155 definition
Serious Adverse Event (SAE)	Refer to ISO 14155 definition
SF-12	A short survey with 12 questions that results in two scales of mental and physical functioning and overall health related quality of life.
Six (6) MWT	Six minute walk test
Stroke/TIA	Refer to VARC-2 definition
Subject	Refer to ISO 14155 definition

Subject Withdrawal	A subject who decides not to participate in the study after signing an informed consent form and being enrolled.
Technical Success	
Technical Success (at exit from procedure room):
 
 • Alive, with • Successful access, delivery and removal of the delivery systems, and • Deployment and correct positioning of the intended device, and • No need for additional emergency surgery or re-intervention related to the device or access procedure
Thromboembolic Event	See “embolism”
Thrombus (Device Thrombosis)	
An aggregation of platelet, fibrin, clotting factors, and other cellular elements exclusive of infection.
 
Device thrombosis is defined as any thrombus in the absence of infection attached to or near the investigational device that interferes with function of the device. An investigational device related thrombus may be confirmed by operation, autopsy, or diagnostically by such methods as echocardiography, angiography, or magnetic resonance imaging.

Tricuspid Regurgitation	Tricuspid Regurgitation (TR), tricuspid insufficiency or tricuspid incompetence describes a condition in which blood flow through the tricuspid valve flows in the incorrect direction during part of the cardiac cycle.
Unanticipated Serious Adverse Device Effect (USADE)	Refer to ISO 14155 definition
Valvular Leak (See Also “Nonstructural Dysfunction”)	Any evidence of leakage of blood through the native valve leaflets and around the investigational device. Diagnosis of valvular leak may be obtained from echo; however definitive diagnosis is obtained at reoperation, explant, or autopsy.
Withdrawal by Investigator	A subject who consents to participate in the study and is enrolled but is withdrawn by the Investigator.

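### The device hemolysis definition requires impaired device function and borrows thrombus wording, so hemolysis caused by a working device falls outside the label

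*Protocol*

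**What the plan says.** The hemolysis entry in protocol Section 19 has three parts.

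- It first defines hemolysis in general: "Rupturing of red blood cells (erythrocytes) and the release of their contents (cytoplasm) into surrounding fluids".
- It then narrows the term for the device: "Device hemolysis is defined as hemolysis in or near the investigational device that interferes with the function of the device".
- It ends on confirmation: "Device hemolysis related thrombus may be confirmed by operation, autopsy, or diagnostically by such methods as echocardiography, angiography, or magnetic resonance imaging".

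The device thrombosis entry in the same section covers "any thrombus in the absence of infection attached to or near the investigational device that interferes with function of the device", and continues: "An investigational device related thrombus may be confirmed by operation, autopsy, or diagnostically by such methods as echocardiography, angiography, or magnetic resonance imaging".

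Section 3.1 lists hemolysis among the additional risks of the FORMA System and attaches no condition about device function. Tables 4, 7 and 8 schedule LDH, bilirubin, hemoglobin, hematocrit and red cell count at baseline, discharge and each follow-up visit.

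SAP Section 3.1 says that adverse event data will be summarized descriptively. The variable list in SAP Section 4 names neither hemolysis nor any of these markers, although it allows parameters to be added.

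**The concern.** Requiring interference with function makes sense for a clot on or near a spacer. It fits red-cell destruction poorly, because there the harm described by the protocol's own general definition is to the blood cells and not to the implant. As written, the label depends on how the device is performing and not on whether the device is destroying red cells. The only diagnostic sentence in the entry concerns a different event.

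What is at stake is the description of one risk that the protocol itself attributes to the device, in a study whose stated purpose is safety and device performance and whose data are meant to support regulatory approval. A device hemolysis count taken from the printed definition would leave out cases in which the implant still works.

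**Working it through.** No figure in the plan depends on this definition, so nothing can be reproduced or recalculated. The check is a comparison of texts, followed by tracing one hypothetical subject through them.

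**1. Hemolysis entry against thrombosis entry (Section 19).** Both impose the same function condition. Their confirmation sentences list the same methods in the same order: operation, autopsy, echocardiography, angiography, magnetic resonance imaging. In the hemolysis entry the grammatical subject of that sentence is thrombus. The likely explanation is that the text was carried over from the thrombosis entry. What remains contains no criterion for detecting hemolysis.

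**2. Hemolysis entry against the risk list (Section 3.1).** The risk is hemolysis, unqualified. The label is hemolysis plus impaired function. The label is therefore narrower than the risk it should track.

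**3. Hemolysis entry against the laboratory schedule (Tables 4, 7 and 8).** Five relevant markers are recorded at baseline and repeatedly afterwards. The definition uses none of them.

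**4. A hypothetical subject.** Suppose that at 1 month an implanted subject is alive with the original device in place, has had no device-related procedure, shows a reduced EROA and has a tricuspid gradient within the 5 mmHg limit. LDH has risen and hemoglobin has fallen from baseline, and the device is the cause.

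- Device Success (Section 5.2.2): met.
- General hemolysis definition (Section 19): met.
- Device hemolysis definition (Section 19): not met, because nothing shows impaired function. The protocol does not define interference with function. Device Success is its nearest measure of performance, and this subject passes it.
- Adverse event (Section 12.2.1): met, since the definition covers "untoward clinical signs (including abnormal laboratory finding) in subjects, users or other persons, whether or not related to the investigational medical device".
- Adverse device effect (Section 12.2.2): met if judged related, since it is "any adverse event related to the use of an investigational medical device". If serious, Section 12.2.4 applies as well.

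The event can be captured and attributed to the device, but not under the device hemolysis label.

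**5. What the event might be called instead.** Section 3.1 offers anemia and abnormal laboratory values, both listed as risks of the overall procedure. Under Section 8.4 implanted subjects generally take aspirin with an anticoagulant or a second antiplatelet agent through 6 months, which gives another possible explanation for a falling hemoglobin. The investigator rates relatedness (Section 12.1) without a laboratory standard for hemolysis.

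**6. Could the analysis recover it?** The SAP variable list includes thrombus among the echocardiographic parameters (SAP Section 4.4), but no hemolysis item and no LDH, bilirubin or hemoglobin summary. A differently labelled event would not reappear in a laboratory table that is now planned.

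**The case against.** The strongest reply is that a glossary label does not control safety reporting. Adverse events include abnormal laboratory findings, an adverse device effect needs only a relation to the device, and neither definition asks for imaging or impaired function. Section 12.2.1 makes the Section 3.1 risks the anticipated events, and hemolysis is there without qualification. The causality rules in Section 19 class cases that cannot be assessed as possible and count a known side effect of the product category toward relatedness. The sponsor and the DMC review adverse events (Section 3.2), and listings cover all enrolled subjects (Section 13.3). All of this stands, and it limits the point to labelling and tabulation.

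A reader might also infer that hemolysis must be proved by imaging or autopsy. The text does not say so: "Device hemolysis related thrombus may be confirmed by operation, autopsy, or diagnostically by such methods as echocardiography" is permissive, lists operation too, and concerns a related thrombus.

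It is also fair to say that LDH and hemoglobin are not specific. Hepatic congestion and bleeding can move them, and the tables name neither haptoglobin nor plasma free hemoglobin. This is a reason to review other causes. It does not justify keeping a function condition that measures something else.

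**Conclusion.** The defect in the definition is real. Device hemolysis is limited to cases that impair the device, carries thrombus wording, has no laboratory criterion, and is narrower than the risk listed in Section 3.1. The consequence is possible under-labelling of a device-specific risk in the adverse event summaries. The primary endpoint, technical, device and procedural success, the clinical outcomes, the hypothesis test and the sample size are unaffected.

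Two stronger readings are not supported. One is that such hemolysis would not be classified as a device event at all; the adverse device effect route remains open. The other is a number of missed cases or a stated bias in a planned rate. The documents give no hemolysis rate, do not say how often hemolysis occurs with a working device, and plan no device hemolysis rate that could be biased. The stopping rules in Section 16 are redacted, so nothing can be said about use of the term there.

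The conclusion assumes only that hemolysis can occur while the device still functions, and that investigators apply the printed definition when choosing the label. The correction is worth making because it is cheap and concerns a named device risk in a safety study.

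**What to change.** - In the hemolysis entry of Section 19, delete the device-function condition and the thrombus confirmation sentence. Impaired function and thrombus can be recorded under their own terms.
- Reconcile the entry with the Section 3.1 risk list: define device hemolysis as device-related red-cell destruction, supported by change from the subject's own baseline in LDH, bilirubin, hemoglobin, hematocrit and red cell count. The sponsor should fix the thresholds before analysis and state how other causes will be reviewed.
- Add hemolysis and these markers, by visit, to the variable list in SAP Section 4.

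The cost is one revised definition and an addition to the SAP tables. The markers named need no new sampling. The downside is that the reported hemolysis rate may be higher, and LDH rises from hepatic congestion or hemoglobin falls from bleeding will need case review.

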20 APPENDIX A - SAMPLE INFORMED CONSENT FORM

21 APPENDIX B - CT ACQUISITION PROTOCOL

22 APPENDIX C - ECHO PROTOCOL

23 APPENDIX D – SCREENING COMMITTEE CHARTER

1. GLOSSARY OF TERMS

The following abbreviations are used throughout the document and shall not be defined elsewhere:

6MWT	6-Minute Walk Test
ADS	Analysis Data Set
AE	Adverse Event
AKI	Acute Kidney Injury
BMI	Body Mass Index
BNP	Brain Natriuretic Peptide
CI	Confidence Interval
CIP	Clinical Investigational Plan
CSR	Clinical Study Report
DMC	Data Monitoring Committee
ECG	Electrocardiogram
eCRF	electronic Case Report Form
EDC	Electronic Data Capture
EROA	Effective Regurgitant Orifice Area
HF	Heart Failure
IC	Informed Consent
IP	Implant population
ITT	Intent-to-treat analysis population
KCCQ	Kansas City Cardiomyopathy Questionnaire
KCCQOS	KCCQ Overall Summary Score
KM	The Kaplan-Meier Method
Max	Maximum
Min	Minimum
MCS	Mechanical Circulatory Support
NYHA	New York Heart Association
PCS-12	Physical Health Summary score
PE	Pericardial Effusion
PP	Per protocol
PPM	Permanent Pacemaker

QoL	Quality of Life
SAE	Serious Adverse Event
SAP	Statistical Analysis Plan
SAS[®]	Statistical Analysis Software
SD	Standard deviation
SF-12	Medical Outcomes Study 12-Item Short-Form Health Survey
SVC	Superior Vena Cava
TV	Tricuspid Valve
TR	Tricuspid Regurgitation
US	United States
VCW	Vena Contracta Width

2. SYNOPSIS OF STUDY DESIGN AND PROCEDURES

2.1 Purpose of the Statistical Analysis Plan

The statistical analysis plan (methodology) provides detailed description of the planned analysis and methodology for Study #2015-09, the SPACER Trial – Repair of Tricuspid Valve Regurgitation using the Edwards FORMA Tricuspid Transcatheter Repair System. This SAP is based on Clinical Investigation Plan Rev C.G.

2.2 Study Objectives

The purpose of the study is to assess the safety and device performance of the Edwards FORMA Tricuspid Transcatheter Repair System in patients with clinically significant, symptomatic, tricuspid regurgitation who are at high surgical risk for standard tricuspid repair/replacement.

2.3 Study Design

This is a multi-center (≤ 12), international, prospective, single arm, safety study designed to assess the safety and device performance of the FORMA System.

A total of seventy-eight (78) subjects will be enrolled in the study. All implanted study patients will be assessed for clinical follow-up at the following intervals: 1 month, 6 months, 1 year and annually for 3 years post implant procedure. Centers that do not have experience with the investigational device will be allowed a single “roll-in” subject to become familiar with the study device and procedure.

2.3.1 Primary Endpoint:

The primary endpoint for the study will assess the all-cause mortality of the as treated cohort at 30 days compared to a literature derived Performance Goal based on high-risk surgical outcomes for tricuspid repair/replacement.

2.3.2 Secondary Endpoints and Clinical Outcomes:

The following secondary endpoints and clinical outcomes will also be assessed:

Technical Success (at exit from procedure room):

- Alive, with
- Successful access, delivery and removal of the delivery systems, and

- Deployment and correct positioning of the intended device, and
- No need for additional emergency surgery or re-intervention related to the device or access procedure

Device Success (at 1 month, 6 months & annually):

- Alive, with
- Original intended device in place, and
- No additional surgical or interventional procedures related to the device, and
- TR reduction (assessment made by change in EROA) compared to baseline and TV gradient $\leq 5\text{mmHg}$

Procedural Success (at 1 month):

- Device Success, and
- None of the following device or procedure related SAEs:
 - Life threatening bleeding
 - Major vascular or cardiac structural complications requiring intervention
 - Pericardial effusion requiring drainage or surgery (includes tamponade)
 - Stage 2 or 3 acute kidney injury (includes new dialysis).
 - Severe heart failure or hypotension requiring IV inotrope, ultrafiltration or mechanical circulatory support
 - Prolonged intubation > 48 hours

Clinical Outcomes (at 1 month, 6 months & annually)

- Re-hospitalization rates for the underlying condition (heart failure)
- Re-intervention rates for the underlying condition (tricuspid regurgitation)
- Change in Tricuspid Regurgitation (assessment made by change in EROA) from baseline
- Change in peripheral edema as assessed by subject weight loss (kilograms) from baseline
- Change in NYHA Class from baseline
- Change in 6 minute walk test distance (meters) from baseline
- Change in Quality of Life as assessed by the SF-12 and KCCQ questionnaires from baseline

2.4 Analysis Populations

The analysis population will be grouped into four analysis cohorts that in total comprise all subjects enrolled in this study. The analysis cohorts are defined below:

- Enrolled Cohort: all subjects enrolled in the study
- As Treated (AT) Cohort: all subjects who are enrolled and undergo the study procedure (chest incision)
- Implanted Cohort: all subjects who undergo the study procedure (chest incision), receive and retain the investigational device upon leaving the procedure room
- Roll-In Cohort: first subject enrolled and treated at a center that does not have previous device or procedure experience and is classified as a “roll-in” subject

The primary endpoint will be reported based on the AT cohort. For the secondary endpoints and clinical outcomes, technical success analysis will be performed for the AT cohort, while device success, procedure success and clinical outcomes analyses will be performed for the implanted cohort. Roll-In subjects will be analyzed separately. Subject listings for adverse events, deaths will include all enrolled subjects.

For subjects with major protocol violations, which include but are not limited to study criteria and informed consent violations, a secondary analysis will be conducted in which those subjects will be excluded from the implanted cohort analyses.

3. STATISTICAL ANALYSIS

3.1 General Considerations

Baseline demographics, medical history, procedural data, adverse event data, and endpoint data will be analyzed using descriptive statistics.

Continuous variables will be summarized using means, standard deviations, medians, ranges, and 95% confidence intervals for the mean based on normal distribution.

Binary variables will be summarized with counts, percentages, and 95% Clopper-Pearson confidence intervals.

Time to event variables will be analyzed using Kaplan-Meier estimates.

Nonparametric techniques may be used if the data does not meet the assumptions of parametric tests.

3.2 Primary Endpoint Analysis

A performance goal of 18% was pre-specified for the 30-day rate of all-cause mortality in TVR (Tricuspid Valve Regurgitation) subjects treated with the Edwards FORMA Tricuspid Transcatheter Repair System, which was based on review of literature and early clinical studies. The hypothesis for the primary endpoint is as follows:

H0: $\pi \geq 18\%$

HA: $\pi < 18\%$

Where π represents the all-cause mortality rate at 30 days.

The primary endpoint for this clinical study is all-cause mortality at 30 days post-implant procedure in the as treated (AT) cohort population. A one-sided 95% confidence interval for 30 day mortality will be computed using the Kaplan-Meier algorithm with the standard errors being computed using Greenwood's formula. The null hypothesis shall be rejected at alpha = 0.05 if the upper confidence limit is less than 0.18.

3.3 Additional Endpoint Analysis

Kaplan Meier estimates will be performed at the pre-specified follow-up times to project the estimates for time-related safety endpoints. The rate of freedom from all-cause mortality at 6 month, 1 year, 2 years, and 3 years will be estimated in addition to the primary endpoint which is established at 30 days post procedure.

Echocardiographic data will be analyzed by a core laboratory. The improvement from baseline for selected items will be presented as shift from baseline for each of the pre-specified follow-up periods. Subjects that are missing a baseline or follow-up values will be excluded from the analysis.

Subjects that undergo any type of repair or replacement procedure for the tricuspid valve will be excluded from the implant cohort analyses at the time of the re-intervention.

The average overall (general) quality of life at baseline, 1 month, 6 months and annually for 3 years and the changes from baseline to follow up will be summarized by mean and standard deviation for the implanted cohort. Patients that are missing a baseline or follow up values will be excluded from the analysis.

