4.3.4 Clinical Outcomes (at 1 month, 6 months & annually)

- Re-hospitalization rates for the underlying condition (heart failure)
- Re-intervention rates for the underlying condition (tricuspid regurgitation) Change in Tricuspid Regurgitation (assessment made by change in EROA) from baseline
- Change in peripheral edema as assessed by subject weight loss (kilograms) from baseline
- Change in NYHA Class from baseline
- Change in 6 minute walk test distance (meters) from baseline
- Change in Quality of Life as assessed by the SF-12 and KCCQ questionnaires from baseline

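### Kaplan-Meier is the plan's only time-to-event method; if it is applied to non-fatal events such as heart-failure re-hospitalization with deaths censored, it overstates them, increasingly to year 3

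*SAP*

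**What the plan says.** SAP Section 3.1 sets a general rule: "Time to event variables will be analyzed using Kaplan-Meier estimates". The same section also provides for binary data: "Binary variables will be summarized with counts, percentages, and 95% Clopper-Pearson confidence intervals".

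SAP Section 3.3, like protocol Section 13.5, adds: "Kaplan Meier estimates will be performed at the pre-specified follow-up times to project the estimates for time-related safety endpoints". The only endpoint named directly after it is mortality: "The rate of freedom from all-cause mortality at 6 month, 1 year, 2 years, and 3 years will be estimated".

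Heart-failure re-hospitalization and tricuspid re-intervention are listed separately as clinical outcomes (SAP Section 4.3.4; protocol Section 5.2.4). They are worded as rates and are due at 1 month, 6 months and yearly to 3 years. On the population, SAP Section 2.4 says: "device success, procedure success and clinical outcomes analyses will be performed for the implanted cohort". No estimator is attached to either outcome.

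Three rules on incomplete follow-up bear on this:
- Subjects leave the implanted-cohort analyses when they have a tricuspid repair or replacement (SAP Section 3.3).
- Explanted subjects are followed for safety only and exit at the 6-month visit (protocol Section 8.10).
- Death is listed there as a study exit.

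Neither document mentions competing risks or cumulative incidence.

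**The concern.** A subject who has died can no longer be admitted for heart failure or have a re-intervention. Kaplan-Meier with deaths censored treats that subject as if the event could still occur later. One minus Kaplan-Meier then estimates the event probability in a hypothetical population in which nobody dies. It is at least as large as the proportion of subjects who will actually have the event, and the gap widens as deaths accumulate.

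The plan itself points to non-trivial mortality. Protocol Section 13.1 plans on a 30-day death rate of 7.5% or less against a goal of 18%. Section 1.1.2 describes a poor prognosis for severe regurgitation. Exclusion criterion 14 removes only non-cardiac disease limiting life expectancy to under 12 months. The data are meant to support regulatory approval (protocol Section 2), so a 3-year event rate that depends on an unstated choice of method should be settled in advance.

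**Working it through.** **The plan's own figure.** The only related number in the documents is the sample size of 63 for the primary endpoint (18% against 7.5%, alpha 0.05, at least 80% power). An exact one-sided binomial test with n = 63 rejects at 6 or fewer deaths, with alpha 0.0487 and power 0.808, so 63 reproduces. It has no bearing on this point: in the primary analysis death is the event, so it has no competing event. The documents give no figure for re-hospitalization, re-intervention or mortality after 30 days.

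**Inputs for the check, all assumed.** Annual death D from 10% to 30%. Annual event E from 5% to 40%, meaning the one-year probability if nobody died. Constant hazards.

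**Formulas.**
- Death hazard d = -ln(1 - D); event hazard h = -ln(1 - E).
- One minus Kaplan-Meier, deaths censored: 1 - exp(-h t).
- Cumulative incidence, death competing: [h / (h + d)] x [1 - exp(-(h + d) t)].

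**Worked example, D = 20%, E = 30%, t = 3 years.**
- d = 0.2231, h = 0.3567, h + d = 0.5798.
- One minus Kaplan-Meier = 1 - 0.7^3 = 65.7%.
- Cumulative incidence = (0.3567 / 0.5798) x (1 - 0.56^3) = 0.6151 x 0.8244 = 50.7%.
- Excess = 15.0 points.

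**Range.** Each cell gives one minus Kaplan-Meier / cumulative incidence, in percent, with the excess in points from unrounded values.

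| Annual death / event | 1 year | 2 years | 3 years |
|---|---|---|---|
| 10% / 5% | 5.0 / 4.7 (0.3) | 9.8 / 8.8 (0.9) | 14.3 / 12.3 (2.0) |
| 10% / 10% | 10.0 / 9.5 (0.5) | 19.0 / 17.2 (1.8) | 27.1 / 23.4 (3.7) |
| 20% / 5% | 5.0 / 4.5 (0.5) | 9.8 / 7.9 (1.9) | 14.3 / 10.5 (3.8) |
| 20% / 20% | 20.0 / 18.0 (2.0) | 36.0 / 29.5 (6.5) | 48.8 / 36.9 (11.9) |
| 20% / 30% | 30.0 / 27.1 (2.9) | 51.0 / 42.2 (8.8) | 65.7 / 50.7 (15.0) |
| 30% / 30% | 30.0 / 25.5 (4.5) | 51.0 / 38.0 (13.0) | 65.7 / 44.1 (21.6) |
| 30% / 40% | 40.0 / 34.2 (5.8) | 64.0 / 48.5 (15.5) | 78.4 / 54.5 (23.9) |

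At 30 days the excess is at most 0.1 point anywhere in the range. For a rare event, as re-intervention may be, the absolute gap is smaller but the relative one is not: with 30% death and 5% event per year, the 3-year values are 14.3% and 8.9%, a factor of 1.61.

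**The case against.** A reader might infer that the plan prescribes Kaplan-Meier, with deaths censored, for heart-failure re-hospitalization and re-intervention, and is therefore wrong as written. The documents do not support that reading.

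- No sentence assigns Kaplan-Meier to either outcome. Both are clinical outcomes, a separate class from the safety endpoints of SAP Section 3.3, and neither is defined as a time to first event.
- They are called rates. They could be reported as percentages with Clopper-Pearson intervals, or as event rates set against the 6-month pre-implant heart-failure hospitalization rate collected at baseline (protocol Section 8.3). If so, one minus Kaplan-Meier is never computed.
- Censoring at death is inferred from usual Kaplan-Meier practice and the absence of any other rule. It is not stated.
- Neither outcome has a hypothesis, threshold or power calculation.
- The size rests on assumed rates. At 1 year the excess is small next to sampling error: with 63 subjects and a proportion near 50%, the 95% half-width is 1.96 x sqrt(0.25 / 63), about 12 points.

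All of this stands, and it makes the point conditional. It does not remove it. The general rule in SAP Section 3.1 is unrestricted, and Section 3.3 speaks of endpoints in the plural. With about 10% dropout allowed for and exits at re-intervention and explant, Kaplan-Meier is the only method in the plan that deals with incomplete follow-up.

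The percentage route is not clean either. SAP Section 3.5 uses only subjects with available data and does not say whether those who died stay in the denominator. If they are dropped, and if hazards are constant and the event does not alter the death hazard, the proportion among survivors is 1 - exp(-h t), the same inflated value. Sampling error does not cancel a systematic excess, and by year 3 the excess can be larger than the half-width above.

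**Conclusion.** The point holds conditionally. The plan gives Kaplan-Meier as its one time-to-event method, does not confine it to mortality, and is silent on death as a competing event. Applied to non-fatal events with deaths censored, that rule overstates their probability whenever deaths occur before the event. The direction does not depend on the assumed rates. The size does: roughly 0.3-6 points at 1 year and 2-24 points at 3 years, for annual death of 10-30% and annual event rates of 5-40% under constant hazards.

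All-cause mortality at every time point, the primary test and the sample size are unaffected. Only descriptive estimates would change. This is a cheap improvement, not an error that undermines the study.

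**What to change.** In SAP Sections 3.1 and 3.3 and protocol Section 13.5:

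- Keep Kaplan-Meier for all-cause mortality.
- For first heart-failure re-hospitalization, re-intervention and other non-fatal time-to-event outcomes, use the Aalen-Johansen cumulative incidence with death as a competing event.
- Count a re-intervention as an event in its own analysis before the subject leaves the implanted cohort.
- For heart-failure re-hospitalization, handle removal at re-intervention or explant explicitly, for example as a further competing event or by continuing to count available follow-up. Do not treat it as ordinary censoring.
- Say whether the re-hospitalization rate means first events or all events. Cumulative incidence answers the first; a count of all admissions needs its own definition.

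The cost is SAP and protocol wording, a standard software option and a little extra analysis work. It needs no new data and places no burden on patients.
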